5.0 Study Intervention/Investigational Agent - N/A

	Applicable to:		
FDA Regulation	IND Studies	IDE studies	Abbreviated IDE studies
21 CFR 11	X	X	
21 CFR 54	X	X	
21 CFR 210	X		
21 CFR 211	X		
21 CFR 312	X		
21 CFR 812		X	X
21 CFR 820		X	

The collared and collarless femoral stem implants that will be used in this study are FDA-approved for standard use in primary THA. The 510(k) number for the collared hip stem is K150862 and for the collarless version is K21058. Thus, both hip prosthetics are not Huds and do not have IDE or HDE numbers. No other investigational drugs or devices will be administered.

6.0 Procedures Involved*

This study is a prospective, randomized controlled trial comparing the clinical and radiographic outcomes of a collared versus collarless femoral stems of the same design in primary THA. A total of 100 participants undergoing elective, uncemented primary THA for degenerative hip disease will be enrolled.

Participants will be randomized in a 1:1 ratio to receive either a collared femoral stem or a collarless femoral stem. All patients indicated for a cementless primary total hip arthroplasty will be offered enrollment. Once consented, they will be randomized into the collared or collarless stem groups. Study participants will be informed about the risk of randomization due to removing the elements of choice from the clinician, as outlined in the informed consent form.

MOD00024127

Page 6 of 18

Revised: November 12, 2025 IRB Approved

12/18/2025 - 11/3/2026

PROTOCOL TITLE: Comparison of clinical and radiographic results of collared and collarless femoral stems in total hip arthroplasty

The primary endpoint is femoral stem subsidence, measured at postoperative 6week, 6-month, and 1-year clinical visits, which coincide with standard of care routine follow-up. Secondary endpoints include the incidence of PPF and aseptic stem loosening within the first postoperative year. Again, all research procedures are designed to align with standard perioperative and postoperative care for THA, minimizing burden for study participants. Additionally, the ACTIS Hip Stem (DePuy Synthes, Warsaw, IN) is routinely used by the participating surgeons for the last 3-4 years. The following outlines the specific protocol steps and time points:

Preoperative (Day -30 to 0):

- Obtain written informed consent either in person or via Interlace.
- Confirm eligibility criteria (inclusion/exclusion).
- Record baseline demographic data, diagnosis, and Dorr classification (from preop imaging).
- Randomization and group assignment.

Operative Day (Day 0):

- THA performed using the allocated femoral stem type (collared or collarless), via a standard surgical approach.
- Per standard practice, intraoperative documentation of any complications, including intraoperative PPFs, will be recorded by the surgical team.

Postoperative Follow-Up:

- Routine anterior-posterior (AP) pelvic and lateral hip X-rays will be obtained at 6 weeks, 6 months, and 1 year.
- Subsidence will be quantified using standardized radiographic measurement techniques. Typically, radiographs are obtained at 6 weeks, 6 months and annually thereafter. Calibration will be performed with the known femoral head size and subsidence measured by standard techniques on these serial radiographs.

Adverse Event Monitoring (Ongoing):

- Any PPFs or aseptic loosening will be identified through clinical assessment, imaging review, and/or surgical reports, and reported by trained investigators or study staff.
- Participants will be advised to report any fall or unusual hip symptoms. Any clinically indicated imaging or intervention will be reviewed for endpoint classification.

Risk Minimization:

- All surgeries will be conducted by experienced orthopaedic surgeons within the MedStar Health System (MedStar Georgetown University Hospital and MedStar Washington Hospital Center) to minimize procedural variability.

MOD00024127

Page 7 of 18

Revised: November 12, 2025 IRB Approved

12/18/2025 - 11/3/2026

PROTOCOL TITLE: Comparison of clinical and radiographic results of collared and collarless femoral stems in total hip arthroplasty

- Standard sterile technique and perioperative protocols will be followed.
- Follow-up visits coincide with routine care to minimize patient burden.
- Radiographic measurements will be conducted by independent reviewers to reduce measurement error and bias.
- There is no additional physical risk to participating in this study beyond standard of care.
- The primary risk is a potential breach of confidentiality. To minimize this risk, all data will be de-identified and stored on password-protected, HIPAA-compliant platforms. Participants will be assigned a unique study ID (SID), and any linkage to identifiable information (e.g., MRN) will be stored separately in a secured, password-protected file. No patient names or identifiers will be recorded on any data collection forms.
- Study participants will be made aware about the risk of randomization for the implant they will receive. By participating in the study, the surgeons will not be able to choose the implant.

Devices Used:

- Collared and collarless femoral stems, both commercially available and FDA cleared for primary THA use—the ACTIS Hip Stem that comes in both a collared and collarless variation, will be used.
- Both stem types are used in current clinical practice and do not represent investigational use.

Source Records:

- Source documentation will include:
 - Electronic medical records (EMR)
 - Operative reports
 - Imaging records (X-rays)
 - Clinic visit notes
- Patient-reported outcome forms—collected in OBERD, the standard platform at MedStar for collecting PROMs

Data Collected:

- Demographics and clinical variables: age, sex, BMI, comorbidities, Dorr classification.
- Operative data: stem type, surgical approach, intraoperative complications.
- Primary endpoint: femoral stem subsidence at 6 weeks, 6 months, and 1 year, measured in millimeters from standardized serial radiographs.
- Secondary endpoints:
 - PPF incidence (confirmed radiographically or operatively).
 - Aseptic loosening (evidenced by radiolucent lines, implant migration, or revision surgery).
- Other outcomes: functional scores (PROMs), adverse events, and reoperation rates.

MOD00024127

Page 8 of 18

Revised: November 12, 2025 IRB Approved

12/18/2025 - 11/3/2026

PROTOCOL TITLE: Comparison of clinical and radiographic results of collared and collarless femoral stems in total hip arthroplasty

Data Collection Methods:

- Radiographic analysis performed by independent reviewers blinded to group allocation.
- Adverse events recorded by research staff at each visit and during any interim visits.

Long-Term Follow-Up — Patients will follow standard protocol for follow-up, offering the possibility of more longitudinal reporting potentially 5-10 years postop.

Humanitarian Use Device (HUD) — N/A

This study does not involve any HUDs. All devices used (collared and collarless femoral stems) are FDA-approved for standard use in primary THA and do not require an Investigational Device Exemption (IDE). The 510(k) number for the collared hip stem is K150862 and for the collarless version is K21058.

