10.0 Inclusion and Exclusion Criteria*

Potential participants will be identified from the MedStar Orthopaedic Surgery clinics at MGUH and MWHC. Screening will occur during routine preoperative consultation visits for patients scheduled to undergo primary, uncemented THA due to osteoarthritis or other non-inflammatory degenerative joint disease.

Patients will be screened by the study investigator or trained research coordinator. Screening will involve review of the EMR for clinical and radiographic eligibility,

MOD00024127

Page 9 of 18

Revised: November 12, 2025 IRB Approved

12/18/2025 - 11/3/2026

PROTOCOL TITLE: Comparison of clinical and radiographic results of collared and collarless femoral stems in total hip arthroplasty

verification of surgical plan, preoperative radiographic assessment, and assessment of patient capacity to provide informed consent. Patients who meet all inclusion criteria and none of the exclusion criteria will be approached for informed consent and formally enrolled after confirming eligibility.

Inclusion Criteria:

- Adults (≥ 18 years old) scheduled for primary, uncemented THA using a cementless femoral stem.
- Diagnosis of primary osteoarthritis or other non-inflammatory degenerative joint disease.
- Ability and willingness to comply with study procedures and follow-up schedule.
- Ability to provide written informed consent.

Exclusion Criteria:

PROTOCOL TITLE: Comparison of clinical and radiographic results of collared and collarless femoral stems in total hip arthroplasty

- **Patients not indicated for a cementless THA.**
 - Prior surgery on the ipsilateral hip (e.g., prior THA, internal fixation, osteotomy).
 - Use of cemented or hybrid femoral components.
 - Revision THA or conversion THA.
 - Active or prior infection of the hip joint.
 - Severe osteoporosis (T-score ≤ -2.5) or known metabolic bone disease.
 - Inability to complete follow-up or anticipated relocation out of the area.

Special Populations:

The following special populations will be excluded from participation in this study: adults unable to provide consent, anyone under the age of 18, and pregnant women.

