13.0 Recruitment Methods

Recruitment will occur during standard preoperative clinic visits at the Department of Orthopedic Surgery at MGUH and MWHC. Potential subjects will be identified weekly by IRB-approved research staff by screening clinic appointments. Patients scheduled for primary, uncemented THA will be approached during these visits. Recruitment will begin after IRB approval and continue until the target enrollment of 100 participants is reached. Each potential participant will be approached in-person by a study investigator or trained research coordinator prior to surgery, typically 2–4 weeks in advance.

The study will be described in detail, and eligible patients will be provided with a written informed consent form and ample time to ask questions. If interested, they may sign the consent form at that time or take it home and return it during a subsequent visit. Patients may also choose to complete an electronic consent form

MOD00024127

Page 11 of 18 Revised: November 12, 2025 IRB Approved

12/18/2025 - 11/3/2026

PROTOCOL TITLE: Comparison of clinical and radiographic results of collared and collarless femoral stems in total hip arthroplasty

that can be sent to their emails through a secure MedStar consenting platform, Interlace.

All subjects will be under the routine clinical care of orthopaedic providers at the study institution and will be recruited without deviation from the standard clinical pathway for surgical planning and follow-up. Recruitment will occur entirely through face-to-face interaction during clinic visits, with no use of public advertisements, social media, or media broadcast. No posters or flyers regarding the study will be distributed.

No monetary compensation will be provided to participants for their involvement in this study.

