14.0 Withdrawal of Subjects*

A subject may choose to withdraw from the study at any time. Withdrawal of a subject will have no effect on their clinical care or clinical decision making.

Subjects may also be withdrawn from the study without their consent under the following circumstances:

- Intraoperative change in surgical plan, such as conversion to a cemented or hybrid femoral stem, revision THA, or significant intraoperative complications rendering the assigned study implant unusable.
- Failure to attend postoperative follow-up appointments necessary for primary or secondary outcome data collection.
- Medical conditions or complications (e.g., infection, stroke, malignancy) that significantly impact the participant's ability to safely continue study participation or follow the protocol.
- Protocol violation identified by the research team that invalidates study participation (e.g., unintentional enrollment of an ineligible subject).

In all such cases, the reason for withdrawal will be documented in the subject's research file and medical record.

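### Stem type may be assigned weeks before surgery with no concealment until theatre, so losses between assignment and implantation can depend on the arm

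*Protocol*

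**What the plan says.** **Timing of assignment.** Section 6.0 states "Once consented, they will be randomized into the collared or collarless stem groups". Its preoperative step, Day -30 to Day 0, lists consent, the eligibility check, baseline data with Dorr class and, last, "Randomization and group assignment". No day within that window is fixed. The operative-day step begins with implanting the allocated stem. Section 13.0 has patients approached "prior to surgery, typically 2–4 weeks in advance".

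**Eligibility.** Section 10.0 includes adults "scheduled for primary, uncemented THA using a cementless femoral stem", which describes the planned operation. One exclusion, "Use of cemented or hybrid femoral components", is worded as actual use.

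**After assignment.** Section 14.0 lets the team withdraw a subject without consent for "Intraoperative change in surgical plan, such as conversion to a cemented or hybrid femoral stem", and also for a serious intraoperative complication that prevents use of the assigned implant.

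**Blinding.** Section 6.0 blinds the radiograph reviewers. The protocol does not say when the surgeon learns the arm, or that the arm is concealed up to any point.

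**The concern.** A surgeon cannot be blind to a collar while implanting the stem. What the protocol can control is how long before implantation the arm is known, and how many decisions are taken with that knowledge. As written, the arm may be known when the operation is postponed, when the fixation plan is reconsidered, and when the femur is judged in theatre.

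Section 2.0 hypothesises that the collar reduces subsidence and fracture. A surgeon who shares that view and faces a doubtful femur has more reason to abandon a collarless assignment than a collared one. Patients lost in this way would plausibly have been among those who subside most. If more of them leave the collarless arm, the measured difference shrinks towards zero. A patient converted to a cemented stem has no film of the assigned stem, so following that patient up cannot supply the missing subsidence value. The problem is better prevented by the timing of assignment than repaired in the analysis.

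**Working it through.** **Step 1: sequence.** The preoperative eligibility check comes first. Randomization follows at an unstated point up to Day 0. Then comes an interval of anything from zero to 30 days, and then surgery, where section 14.0 anticipates conversions. The exposed interval is the one between randomization and implantation.

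**Step 2: the plan's own figure.** Section 17.0 gives 20 per group for a difference of 0.4 mm, SD 0.45 mm, 80% power and α = 0.05 (taken as two-sided).

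n = 2 × (1.960 + 0.842)² × (0.45/0.4)² = 2 × 7.849 × 1.2656 = 19.9, so 20 per group.

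This reproduces. A t-test calculation gives 21 per group, and 78.2% power at 20. The 0.4 mm and 0.45 mm therefore serve as yardsticks below.

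**Step 3: a ceiling on the bias.** The documents give no conversion or withdrawal rate, so the counts lost are assumptions. Take 50 per arm (section 12.0) and normally distributed subsidence with SD 0.45 mm, and suppose the k patients lost are exactly the k who would have subsided most. With w = k/50 and z the upper-w normal quantile, the arm mean falls by 0.45 × φ(z)/(1 − w).

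| k lost of 50 | w | z | φ(z) | fall in arm mean (mm) |
|---|---|---|---|---|
| 1 | 0.02 | 2.054 | 0.0484 | 0.022 |
| 2 | 0.04 | 1.751 | 0.0862 | 0.040 |
| 4 | 0.08 | 1.405 | 0.1487 | 0.073 |
| 5 | 0.10 | 1.282 | 0.1755 | 0.088 |

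Net bias, collarless v collared losses:

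- 2 v 1: 0.040 − 0.022 = 0.018 mm, and 0.018/0.4 = 4.5%
- 4 v 1: 0.073 − 0.022 = about 0.05 mm, and 0.05/0.4 = about 12%
- 5 v 1: 0.088 − 0.022 = about 0.065 mm, and 0.065/0.4 = about 16%

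Simulating samples of 50 gives 0.018, 0.050 and 0.065 mm.

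**Step 4: imperfect selection.** If the lost patients lie only 1 SD (0.45 mm) above those who remain, the arm mean falls by (k/50) × 0.45. The net bias is then (1/50) × 0.45 = 0.009 mm (2%) for 2 v 1, (3/50) × 0.45 = 0.027 mm (7%) for 4 v 1, and (4/50) × 0.45 = 0.036 mm (9%) for 5 v 1.

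**The case against.** **Eligibility.** A reader might infer that eligibility itself is settled only in theatre. The protocol does not support this. Section 6.0 puts the eligibility check before randomization, and section 10.0 bases inclusion on the scheduled cementless operation. Section 10.0 also requires preoperative radiographic assessment and excludes patients not indicated for a cementless hip, those with a T-score of −2.5 or below, and those with metabolic bone disease. Many doubtful femurs should therefore be gone before assignment. What theatre settles is receipt of the assigned stem and retention in the study.

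**Knowledge of the arm.** A reader might also infer that surgeons and patients know the arm for weeks. That is permitted but not stated. The 2–4 weeks in section 13.0 is when patients are approached; they may take the form home, and the window already allows assignment on Day 0. The objection stands in this respect: the defect is that the protocol leaves early, open assignment possible.

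**Size.** One could suppose that converted patients would have subsided 1.5 mm more than the rest. Losses of 4 v 1 would then give (3/50) × 1.5 = 0.09 mm, and 5 v 1 would give 0.12 mm, or 23% and 30% of 0.4 mm. This does not fit the protocol's own SD. With 5 of 50 such patients, that subgroup alone contributes an SD of 1.5 × √(0.1 × 0.9) = 0.45 mm, leaving no variation among the other 45. The ceiling in the working is about half as large. It is true that section 17.0 takes its SD from RSA studies. If true migration varies more than that, the ceiling rises in proportion.

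**Analysis as randomized.** Keeping converted patients in follow-up would preserve the fracture, PROM and reoperation comparisons, and an SAP not shown may provide for this. It would not supply subsidence of a stem that was never implanted.

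**Conclusion.** The point holds as one about timing and concealment. The protocol allows assignment at any time from consent to Day 0, describes no concealment until theatre, and foresees surgeon-judged changes of plan followed by withdrawal. Together these let the number and kind of patients with a measurable study stem depend on the arm. The sentence on randomizing after consent is not wrong alone; the exposure comes from combining it with section 14.0.

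The size is unknown. The 4–16% range assumes 50 per arm, normal subsidence with SD 0.45 mm, invented loss counts, and perfect selection of the worst subsiders; less selective loss gives smaller values. The direction, towards no difference, assumes that the collarless arm loses more. The bias is probably modest, but it is cheap to reduce before enrolment and cannot be undone for subsidence afterwards.

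**What to change.** In section 6.0, keep consent, confirmation of eligibility and Dorr grading in the Day -30 to Day 0 step, and move randomization and group assignment to Day 0. State that the assignment is concealed (sealed envelope or electronic release) and opened in theatre only after the surgeon has reconfirmed the cementless plan. Patients whose plan changes before that point are not randomized and are replaced, so the target of 100 should count randomized patients. Align the randomization sentence in section 6.0 with this.

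**Cost.** Protocol wording, a release procedure in theatre, and both stem versions on hand for each case.

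**What remains.** Changes of plan after assignment still fall under section 14.0, so the fix narrows the exposed interval without closing it.

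**An option for the sponsor to weigh, outside the core fix.** Opening the assignment only after the final broach would protect the subsidence comparison further. It would also take fractures during broaching out of the randomized comparison, although SA3 in section 2.0 sets out to compare intraoperative fractures and section 3.0 names their poor capture as a gap the trial should fill.

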4.0 Study Endpoints*

Study Endpoints

- Primary: Measurement of femoral stem subsidence at 6 weeks, 6 months, and 1-year post-operation

MOD00024127

Page 5 of 18

Revised: November 12, 2025 IRB Approved

12/18/2025 - 11/3/2026

PROTOCOL TITLE: Comparison of clinical and radiographic results of collared and collarless femoral stems in total hip arthroplasty

- Secondary: Incidence rates of periprosthetic fractures, incidence rates of aseptic loosening, and patient-reported outcome measures (PROMs)—collected in OBERD.

Safety Endpoints – N/A

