9.0 Study Timelines*

Each participant will be involved in the study for approximately 1 year, from the time of surgery through standard postoperative care. Data will be collected at preop, 6 weeks, 6 months, and 1-year post-op, coinciding with already scheduled clinic visits. The anticipated amount of time to enroll all subjects is 1 year, with the total duration of the project estimated to be 2 years.

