15.0 Risks to Subjects*

Since this study aligns with standard of care for THA procedures, and no investigational devices or additional interventions are introduced beyond routine care, participation in the research carries minimal risk. However, the following potential risks and inconveniences apply:

Physical Risks:

- Radiation exposure from X-rays: Although all imaging is part of routine clinical follow-up and not performed solely for research purposes, participants will

MOD00024127

Page 12 of 18 Revised: November 12, 2025 IRB Approved

12/18/2025 - 11/3/2026

PROTOCOL TITLE: Comparison of clinical and radiographic results of collared and collarless femoral stems in total hip arthroplasty

- undergo three radiographic evaluations (6 weeks, 6 months, and 1 year). The radiation dose is low and well within accepted clinical safety standards.
- Standard surgical risks: These include pain, infection, dislocation, periprosthetic fracture, implant loosening, nerve or vascular injury, and deep vein thrombosis (DVT). However, these risks are inherent to any THA procedure and are not elevated by study participation.
- Increased awareness of complications: Participation may involve increased attention to postoperative outcomes, which could potentially lead to increased anxiety regarding complications.
- Risk of randomization: This study removes the elements of choice from the practicing surgeon. Currently, there is no definitive data based on prospective studies that suggests that one is better than the other. While improvement of symptoms is expected for both implants for all patients, there may be general differences in the clinical and radiographic results between the two.

Psychological and Social Risks:

- There are no direct psychological risks anticipated, but some participants may experience mild anxiety related to study participation, data monitoring, or followup imaging results.
- Privacy risks are minimal due to the use of secure, HIPAA-compliant data systems and appropriate de-identification of research data.

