17.0 Data Management* and Confidentiality

Femoral stem subsidence will be the primary outcome, measured in millimeters at 6 weeks, 6 months, and 1 year postoperatively. Differences in mean subsidence between the collared and collarless groups will be assessed using independent samples t-tests or nonparametric alternatives if assumptions of normality are not met. Incidence of PPF and aseptic loosening will be compared using chi-square tests or Fisher's exact tests. Logistic regression or Cox proportional hazards modeling will be used to adjust for covariates such as age, BMI, Dorr classification, and surgical approach if sample size allows. A sample size of 20 participants per group (40 total) provides 80% power to detect a difference of 0.4 mm in mean stem subsidence, assuming a standard deviation of 0.45 mm (based on prior RSA-based studies), with $\alpha = 0.05$. A proposed target enrollment of 100 participants is set to account for unforeseen dropouts.

All study team members will be trained in HIPAA compliance and Good Clinical Practice (GCP). Electronic data will be stored in a secure, password-protected, encrypted research database hosted on institutional servers. Subject identifiers (e.g., name, MRN) will be stored separately from study data and linked only via a unique coded identifier. Transmission of data between team members or collaborators will occur via encrypted institutional email or secure file-sharing platforms. No data will be shared externally without IRB and institutional approval.

Information Included:

- Demographic data, medical history, surgical details, implant type, radiographic images and measurements, and clinical outcomes (e.g., fracture, loosening, revision surgery).

Storage Location and Method:

- Data will be stored on secure, password-protected, encrypted institutional servers.
- Only authorized members of the research team listed on the IRB application will have access.
- The PI will oversee access and approve any data sharing requests.

18.0 Provisions to Monitor the Data to Ensure the Safety of Subjects – N/A

This proposed research study does not involve more than minimal risk to subjects, since it aligns with standard of care for THA procedures.

MOD00024127

Page 14 of 18 Revised: November 12, 2025 IRB Approved

12/18/2025 - 11/3/2026

PROTOCOL TITLE: Comparison of clinical and radiographic results of collared and collarless femoral stems in total hip arthroplasty

-

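### The first postoperative film named is at 6 weeks, so the 6-week primary subsidence value has no reference and the later values would be changes from week 6 only

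*Protocol*

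**What the plan says.** Protocol section 4.0 defines the primary endpoint as "Measurement of femoral stem subsidence at 6 weeks, 6 months, and 1-year post-operation". Section 6.0, under Data Collected, repeats it as "femoral stem subsidence at 6 weeks, 6 months, and 1 year, measured in millimeters from standardized serial radiographs", and section 17.0 uses the same three time points for the analysis.

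The film schedule is in section 6.0, under Postoperative Follow-Up: "Routine anterior-posterior (AP) pelvic and lateral hip X-rays will be obtained at 6 weeks, 6 months, and 1 year". The next item describes routine practice the same way, "Typically, radiographs are obtained at 6 weeks, 6 months and annually thereafter", and then has "subsidence measured by standard techniques on these serial radiographs". The operative-day steps in that section cover the operation and the recording of complications, but no film. The only earlier imaging named is preoperative and serves the Dorr classification.

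Two other sections agree with this schedule. Section 15.0 says participants will "undergo three radiographic evaluations (6 weeks, 6 months, and 1 year"). Section 9.0 says "Data will be collected at preop, 6 weeks, 6 months, and 1-year post-op". Neither need be a complete list, but neither supplies an earlier postoperative film.

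Section 17.0 claims "80% power to detect a difference of 0.4 mm in mean stem subsidence" with 20 per group and an SD of 0.45 mm. It does not tie the 0.4 mm to a time point or a reference.

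**The concern.** Each subsidence value needs two films: one at the time point and one earlier, with the stem in place. Three films that start at week 6 give at most two changes, but the protocol claims three primary values. The preoperative film cannot serve as reference because no stem is present.

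The missing weeks matter. In section 3.0, the one comparison with a stated time and size is a randomised RSA trial with a mean difference of 2.23 mm at two weeks, which diminished by one year. If a collar acts mainly by limiting early settling, a week-6 reference discards the period in which it acts. Section 3.0 also cites lower average subsidence with a collar over 6 to 18 months, so it would be wrong to assume that the whole effect is over by week 6. The split is unknown.

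The harm may also be irreversible. If no early film is kept for a patient, that patient's migration before week 6 cannot be recovered, and an analysis plan written later cannot repair it.

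**Working it through.** **1. What the schedule can deliver.** Let D(a→b) be the between-arm difference in mean migration from time a to time b. Then

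D(surgery→1 year) = D(surgery→6 weeks) + D(6 weeks→1 year).

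| Primary value | Reference available among the films named | What is estimated |
|---|---|---|
| 6 weeks | none | nothing |
| 6 months | 6-week film | D(6 weeks→6 months) |
| 1 year | 6-week film | D(6 weeks→1 year) |

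The term D(surgery→6 weeks) is lost.

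**2. Which way the rest may point.** Assume the background RSA trial measured from about the time of surgery (the protocol does not say). A difference of 2.23 mm at two weeks that is smaller at one year means that the increment between those times runs against the collar. How much of that increment falls after week 6 is unknown, so dilution, disappearance and reversal are all possible.

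**3. The protocol's own sample size.** Inputs from section 17.0: difference 0.4 mm, SD 0.45 mm, α = 0.05 (taken as two-sided), power 80%.

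n per group = 2 × (1.960 + 0.842)² × (0.45/0.4)² = 2 × 7.85 × 1.266 ≈ 19.9, so 20.

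This reproduces the stated 20 per group. With the t distribution, power at 20 per group is 78% and 21 per group are needed, a trivial difference. At the planned 50 per group, power for the full 0.4 mm is 99%.

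**4. Illustration of a week-6 reference.** Assume that 0.4 mm is the total contrast from surgery and that a share s of it arises after week 6. The t-test has noncentrality (0.4 × s / SD) × √(n/2). With n = 50 and SD 0.45 this is (0.4/0.45) × 5 × s = 4.44 s, on 98 degrees of freedom. Two-sided power at α = 0.05:

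| Share s | Contrast (mm) | n = 50, SD 0.45 | n = 50, SD 0.30* | n = 50, SD 0.60* | n = 40*, SD 0.45 | n = 20, SD 0.45 |
|---|---|---|---|---|---|---|
| 100% | 0.4 | 99% | >99% | 91% | 98% | 78% |
| 50% | 0.2 | 60% | 91% | 38% | 50% | 28% |
| 25% | 0.1 | 20% | 38% | 13% | 17% | 11% |
| 0% | 0 | 5% | 5% | 5% | 5% | 5% |

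n is per arm. Starred values are assumptions (40 per arm is 20% dropout), as are all the shares. Only 0.4 mm, 0.45 mm, 20 and 50 come from the protocol.

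**5. Contrast needed after week 6 for 80% power.** At 50 per arm and SD 0.45 mm it is 0.255 mm, or 0.255/0.4 = 64% of the planned contrast. It is 0.17 mm at SD 0.30 and 0.34 mm at SD 0.60. At 40 per arm and SD 0.45 it is 0.285 mm (71%).

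**6. Reversal.** If the contrast after week 6 is −0.1 mm (a quarter of 0.4 mm, in the other direction), with 50 per arm and SD 0.45, the chance of a significant result is 0.1% in favour of the collar and 19.5% against it.

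**The case against.** The strongest reply is that the protocol makes subsidence at 6 weeks a primary value, which only makes sense if an earlier film is assumed. Section 6.0 says procedures follow standard perioperative care and lists imaging records as source documents without a time limit, so an in-hospital film may well exist. On this view the gap is one unwritten sentence and nobody intends a week-6 reference.

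The possibility stands, and site practice cannot be seen from the protocol. But no section says that such a film is taken, requires it for every patient or makes it the reference, and section 6.0 ties the measurement to the set of films that starts at 6 weeks. Even where early films exist, two sites with independent reviewers could use different references for different patients, and the values would then not be comparable.

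A second reply is that the calculation of change may be set out in an analysis plan not shown. That may be so for the calculation. Which films are acquired and kept has to be fixed in the protocol.

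A third reply is that the power figures run from 5% to over 99% and so do not measure the defect. That is fair: they show how much hangs on an unknown share and are not an estimate of the loss. Finally, the listed schedules agree with each other. They need the same addition in each place; they do not conflict.

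**Conclusion.** The concern holds. The film schedule as stated cannot deliver the primary endpoint as stated: one of the three primary values has no reference, and the other two would exclude migration before week 6. The 0.4 mm power statement would not describe that contrast.

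The size of the loss cannot be derived from the protocol. Under the assumptions above, the planned 50 per arm keep 80% power only if about 64% of the 0.4 mm arises after week 6 (42% at SD 0.30, 85% at SD 0.60). Confidence is medium, because a usable routine film may exist at the sites. The point must nevertheless be fixed before patients are operated on, since it concerns the primary endpoint and early films that were not kept cannot be recovered.

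**What to change.** In sections 4.0 and 6.0, define the endpoint along these lines:

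> *Subsidence at 6 weeks, 6 months and 1 year is the change in stem position (mm) from the first postoperative film already taken in routine care before discharge.*

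Add that film to the data collected in section 6.0, apply the same femoral-head calibration to it, and count patients without one as missing for the primary endpoint. Amend the schedules in sections 6.0, 9.0 and 15.0 to match.

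If the sites take no such film in routine care, drop the 6-week value as an outcome and restate the primary endpoint as migration from 6 weeks to 1 year. State that early subsidence is not measured and that the 0.4 mm power statement in section 17.0 does not apply to this contrast.

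The first route costs a short amendment and one more existing film per patient to measure, with no extra visit, procedure or participant. The fallback costs more: a redefined primary endpoint, a narrower claim, and unknown power until a new power statement is written.
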